#### 5.3.4 Study Drug Dose Interruptions and Dose Modification for Toxicity

Subjects on a BID PTC299 treatment schedule who inadvertently have a delay in administration of a dose of the study drug of  $< 6$  hours should take the planned dose as soon as possible after the intended time of administration. For subjects who inadvertently have a delay in administration of study drug of  $\geq 6$  hours, the dose should not be taken. Study drug administration may continue but the missed dose should not be made up and the planned timing of subsequent study drug dosing should not be altered.

For subjects on a TID PTC299 treatment schedule who inadvertently have a delay in administration of a dose of the study drug of  $\leq 1$  hour, the planned dose should be taken with no changes to the subsequent dose schedule. For subjects who have a delay of  $>1$  hour but  $\leq 4$  hours, the planned dose should be taken; however, all future doses for that day should be shifted later by a corresponding amount. It is recommended that subjects take the last dose of study medication no later than 12:00 midnight on any study treatment day. For example if the 07:00 AM dose is taken at 10:00 AM, the next dose should be taken at 5:00 PM, and the last dose should be taken at 12:00 midnight. For subjects who have a delay in administration of study drug of  $>4$  hours, the dose should not be taken. Study drug administration may continue but the missed dose should not be made up and the planned timing of subsequent study drug dosing should not be altered.

Vomiting upon dose administration is considered as a missed dose; the dose should not be made up and the planned timing of subsequent study drug dosing should not be altered.

Because of a case of liver injury in a patient with a history of prior drug induced liver injury, laboratory parameters reflective of liver injury should be monitored closely. If criteria for DLT are observed based on monitoring ALT, AST, or bilirubin, PTC299 treatment should be held and the parameters (plus alkaline phosphatase) should be retested within 72 hours. If retesting does not confirm DLT-severity abnormalities, PTC299 treatment may be resumed. If the retesting confirms DLT-severity abnormalities, the AMC and PTC Therapeutics medical monitors should be notified. Efforts should be made to investigate the possibility of new or progressive hepatic tumor. Follow-up evaluations of liver-related laboratory parameters (ALT, AST, bilirubin, alkaline phosphatase) should be performed at least 2 times per week, until they are stable or resolved. Further workup may be considered in consultation with the AMC and PTC Therapeutics medical monitors. Further workup may include: obtaining a history of recent symptoms/illnesses and of relevant past history (e.g., history of hepatitis or of hepatitis A or hepatitis B vaccination); obtaining information regarding concomitant drug use (prescription and nonprescription medications, dietary supplements, alcohol consumption, illicit drug use, special diets); questioning the patient regarding potential exposure to environmental toxins; ruling out viral hepatitis A, B, C, D (if hepatitis B is positive), and E, autoimmune hepatitis, alcoholic hepatitis, nonalcoholic steatohepatitis, hypoxic/ischemic hepatopathy, and biliary tract disease; obtaining additional tests to evaluate liver function (e.g., PT, aPTT, INR, albumin); and considering gastroenterology or hepatology consultation [138].

If on-treatment serum ALT, AST, or bilirubin level doubles from baseline, in the absence of a similar change alkaline phosphatase, but has not reached the DLT levels described above, tests for ALT, AST, bilirubin, and alkaline phosphatase should be monitored closely (e.g., at least once per week). PTC299 treatment may continue while the laboratory tests are being performed.

If a subject experiences a DLT during the 28-day course of PTC299 therapy, then study drug administration can be omitted, as necessary, until the adverse event resolves or stabilizes to an acceptable degree (i.e., to < Grade 2). Thereafter, the dose of PTC299 for the remainder of the treatment course during that cycle should be reduced by one dose level; reduction to Dose Level -1 (20 mg/dose BID) may be made for subjects experiencing PTC299-related DLT at Dose Level 1 (40 mg/dose BID); and reduction to Dose Level 4 (100 mg/dose BID) may be made for subjects experiencing PTC299-related DLT at Dose Level 5 (120 mg/dose TID) and reduction to Dose Level 6 (160 mg/dose TID) may be made for subjects experiencing PTC299-related DLT at Dose Level 7 (200 mg/dose TID). Doses during missed days of treatment should not be made up (e.g., if a subject experiences an AE on Day 7 of the treatment course and the event lasts for 3 days, the reduced dose should be administered only for a further 18 days so that the total treatment course duration remains 28 days).

A new cycle of PTC299 treatment may begin when AEs or laboratory abnormalities have returned to baseline levels. If AEs or laboratory abnormalities are not resolved to baseline, week-by-week delays in initiating the new cycle of treatment should be instituted. If it takes longer than 4 weeks for the AE to resolve to baseline, protocol treatment will be permanently discontinued. Once all toxicities have returned to baseline, the next cycle of therapy can be initiated.

Subjects experiencing any of the DLTs described in Section 5.3.3 in the current cycle of therapy should have the dose in the next cycle of therapy reduced by 1 dose level; reduction to Dose Level -1 (20 mg/dose BID) may be made for subjects experiencing PTC299-related DLT at Dose Level 1; reduction to Dose Level 4 (100 mg/dose BID) may be made for subjects experiencing PTC299-related DLT at Dose Level 5 (120 mg/dose TID) and reduction to Dose Level 6 (120 mg/dose TID) may be made for subjects experiencing PTC-related DLT at Dose Level 7 (160 mg/dose TID).

In general, after a dose is reduced for PTC299-related toxicity it should not be re-escalated, even if there is minimal or no toxicity with the reduced dose. However, if further evaluation reveals that the adverse event that led to the dose reduction was not study drug-related, the dose may be re-escalated to the original dose level.

When there is a dose modification, the subject should be notified of the change in dose and the appropriate clinic staff should instruct the subject about the revised number of study medication capsules to be used per dose according to the new dose level.

Clinical use of other anti-VEGF compounds (e.g., bevacizumab) can be associated with delayed wound healing. For this reason, subjects who require surgery or a deep invasive procedure should have PTC299 held for  $\geq 2$  weeks before the procedure, if possible, and PTC299 should be held for  $\geq 2$  weeks after the procedure, or until complete wound healing, to avoid the theoretical risk of impaired wound closure.

#### 5.3.5 Treatment in Phase 2

Once the safety profile at each dose level has been established based on first cycle DLTs in Phase 1, up to 21 additional subjects whose response to treatment can be evaluated will be enrolled in the Phase 2 portion of the study at the highest safely tolerated dose established in the Phase 1 portion to better define the safety, antitumor activity and biological activities of PTC299 at this dose level. In the Phase 2 portion of the study, Simon's 2-stage design will be used, as described in Section 11.1. Treatment will consist of 4 week cycles of therapy (56 or 84 doses) as described in Section 5.3.2. The maximum duration of treatment is 12, 4-week cycles. Definitions of DLT will be as described in Section 5.3.3. Study drug interruptions and dosage reductions will be managed as described in Sections 5.3.1 and 5.3.4.

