## 5.3 Dosing

### 5.3.1 PTC299 Treatment

Each cycle with the study drug includes administration of 56 to 84 doses of PTC299 during a 4-week (28-day) period. The maximum duration of treatment is 12, 4-week cycles. PTC299 will be administered on a BID or TID schedule at approximately the same times each day. At each dose administration, the capsule number corresponding to the appropriate dose level of PTC299 is to be swallowed whole with a glass of tap water (150 to 200 mL). Subjects should be instructed not to bite or chew on the capsules. In case of breakage of the capsules in the oral cavity, an additional glass of water should be taken immediately.

On Day 1 and on Day 28 of cycle 1, the drug will be administered in the clinic with dosing appropriately timed relative to blood sampling for PTC299 PK. Thereafter, subjects will be given an adequate supply of capsules to take at home for the duration of each single cycle (28 days) of treatment.

Ideally, when given BID, doses should be taken at ~12-hour intervals (e.g., at ~7:00 AM and at ~7:00 PM) and, when given TID, PTC299 doses should be taken at ~8-hour intervals (eg, at ~7:00 AM, at ~3:00 PM, and at ~11:00 PM). If convenient for the subject, the drug may be taken during or within ~30 minutes after a meal; however, administration with food is not required. Yogurt or pudding may be taken together with the capsules in case of difficulty in swallowing. While it is realized that variations in dosing schedule may occur in the outpatient setting, the prescribed regimen (dosing intervals) should be followed as closely as possible, especially in the clinic. In particular, on study days of PK profiling, patients administered TID dosing should take the first dose immediately after the pre-dose blood draw and not dose again until all profile blood draws are completed.

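### On the protocol's example three-times-daily schedule, the late-dose rule in section 5.3.4 gives different clock times from its own worked example and runs past the recommended midnight limit

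*Combined protocol and SAP*

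**What the plan says.** Section 5.3.1 asks for TID doses at intervals of about 8 hours and illustrates this with one set of clock times: "eg, at ~7:00 AM, at ~3:00 PM, and at ~11:00 PM". It is the only TID clock schedule in the document.

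Section 5.3.4 then deals with late TID doses according to the length of the delay:

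- Up to 1 hour: "the planned dose should be taken with no changes to the subsequent dose schedule".
- More than 1 and up to 4 hours: the late dose is still taken, but "all future doses for that day should be shifted later by a corresponding amount".
- More than 4 hours: the dose is omitted and later doses keep their planned times.

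The same paragraph adds a recommendation: "It is recommended that subjects take the last dose of study medication no later than 12:00 midnight on any study treatment day". Its worked example is a first dose taken 3 hours late: "if the 07:00 AM dose is taken at 10:00 AM, the next dose should be taken at 5:00 PM", with the last dose at midnight.

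Section 5.3.1 also says that, on PK profile days, a TID subject takes the first dose straight after the pre-dose draw and takes no further dose until the profile draws are finished. Section 4.2.3 places the last of those draws 8 hours after the morning dose.

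**The concern.** The rule, the recommendation and the example stand next to each other and read as one instruction, yet a site that applies the rule and a site that copies the example will tell the same subject different things. The example does not follow from the rule. On the printed times, the rule also cannot be followed without going past the midnight recommendation.

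The paragraph governs both Stage 3 escalation levels (160 and 200 mg/dose TID) and the 120 mg/dose TID fallback. What is at stake is uniform dosing instructions and intervals at those levels, and knowing afterwards what subjects did. The compliance log in Appendix XI records the number of pills by date and by morning, afternoon or evening, without clock times. It would not show which reading a subject followed at home, and it does not say which row a 2 AM dose belongs to.

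**Working it through.** **Inputs.** Planned TID times of 7:00, 15:00 and 23:00 (section 5.3.1, given as approximate examples). Rule range 1 < d ≤ 4 hours, midnight recommendation and worked example (section 5.3.4).

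**1. Can the example be reproduced?** Reading the rule as an equal shift, new time = planned time + d. With d = 3 hours:

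| Dose | Planned | Rule (+3 h) | Example | Shift in example |
|---|---|---|---|---|
| First | 7:00 | 10:00 | 10:00 | 3 h |
| Second | 15:00 | 18:00 | 17:00 | 2 h |
| Third | 23:00 | 02:00 next day | 24:00 | 1 h |

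The rule keeps 8-hour gaps; the example has 7-hour gaps. The example is not reproduced.

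**2. Does a midnight cap explain it?** Shifting by 3 hours and capping the last dose at midnight gives 10:00, 18:00 and 24:00. The second dose is still 18:00, not 17:00. Splitting the remaining time evenly, (24 − 10)/2 = 7 hours, does give 17:00 and 24:00, but the text states no such rule.

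**3. Can the rule meet the midnight recommendation?** On the printed schedule the third dose falls at 23 + d, so 23 + d ≤ 24 requires d ≤ 1. The rule applies only when d > 1.

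| Delay of first dose | Third dose under the rule |
|---|---|
| 1.5 h | 00:30 |
| 2 h | 01:00 |
| 3 h | 02:00 |
| 4 h | 03:00 |

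None meets it. For another planned first dose at time t, with 8-hour gaps, the largest delay that fits is 24 − (t + 16) hours: 2 hours for a 6:00 start, 3 hours for 5:00 and 4 hours for 4:00. The result in this step therefore depends on the 7 AM schedule.

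**4. PK profile days.** If a first dose were taken at 10:00 on a profile day, the 8-hour draw would fall at 10:00 + 8 h = 18:00. The example's 17:00 dose would come before it, against section 5.3.1. The rule's 18:00 dose would coincide with it.

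**5. How much could the next pre-dose level differ?** The shift applies to that day only, so the next dose is again due at 7:00. The time since the last dose is then 5 hours under the rule, 7 hours under the example and 8 hours on schedule.

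Section 1.2.6.2, Table 2, gives no half-life. A rough value can be taken from the Day 7 TID group means: 4.65 µg/mL at 2.33 hours, and a C24h of 2.37 µg/mL, assumed to be 8 hours after the last dose. Then (8 − 2.33) × ln 2 / ln(4.65/2.37) = 5.83 hours. With equal doses, a single exponential decline and earlier days on schedule, each dose contributes 2^(−elapsed hours/5.83):

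- Rule (21, 13 and 5 hours elapsed, plus earlier days): 0.082 + 0.213 + 0.552 + 0.036 = 0.883.
- Example (21, 14 and 7 hours elapsed, plus earlier days): 0.082 + 0.189 + 0.435 + 0.036 = 0.742.
- Ratio: 0.883/0.742 = 1.19.

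Counting only the last dose would give 2^(2/5.83) = 1.27, which overstates the difference because earlier doses also contribute. The same sum over all doses gives about 1.51 with a 3-hour half-life (the distribution phase in section 1.2.6.1) and 1.00 to 1.01 with 28 to 56 hours (the terminal phase there).

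**The case against.** The strongest reply is that the text says a corresponding amount, not an equal one. Read in order, the paragraph gives the rule, then the midnight recommendation, then an example that meets that recommendation with all three doses evenly spaced. For a 3-hour delay of a 7 AM dose, a site has explicit times to follow, and what is missing is only a formula for other delays. This has some force: the example and the recommendation agree with each other. But nothing tells a site to shrink the shift from 3 hours to 2 and then to 1, and neither an equal shift nor a capped one yields 5 PM.

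The other limits on the point also stand. The clock times are approximate examples of an ideal, and the midnight line is advice. A reader might infer that the rule can never satisfy the midnight line; that is true on the printed schedule but not for every earlier start.

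A reader might also infer harm to the Stage 3 MTD. Sections 5.3.2 and 5.3.3 set the MTD from first-cycle dose-limiting toxicities, and no route is shown from an occasional late dose to those counts. Nor does the text tell anyone to skip a shifted third dose: omission applies to a delay of more than 4 hours, and both the rule and the example deliver all three doses. On-treatment pre-dose samples are few (Days 15 and 28 of cycle 1, and Day 28 of cycle 2 or Day 1 of cycle 3), so a late dose matters to them only if it falls shortly before one.

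**Conclusion.** The inconsistency is real and rests on clock arithmetic alone. For a 3-hour delay of the first dose on the printed schedule, the rule and the example differ by 1 hour at the second dose (6 PM against 5 PM) and 2 hours at the third (2 AM against midnight). This takes the corresponding amount to be the length of the delay. On that schedule, every first-dose delay covered by the rule also takes the last dose past the recommended midnight limit.

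The practical consequence is that subjects at the Stage 3 TID levels may be given different times and intervals. The documents do not support a stronger claim about the MTD, sample size, error rates or lost doses, and they do not say how often doses run late. The effect on a pre-dose level cannot be fixed at one figure: the ratio ran from about 1.0 to 1.5. The top of that range treats the short distribution phase as the whole decline, although section 1.2.6 describes two-compartment kinetics with a long terminal phase. The effect is therefore uncertain and likely small. This is a wording fault in an operative dosing instruction, worth correcting because it is cheap to correct.

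**What to change.** The sponsor and the medical monitors should reconcile the shift rule, the midnight recommendation and the worked example in section 5.3.4 so that all three give the same times. The revised text should make clear how it works for delays other than 3 hours, for planned times other than 7 AM, and when a shifted dose would pass midnight. It should also be checked against the PK-day instruction in section 5.3.1, so that the two do not conflict when a profile day starts late. Which timing is right is for them to decide; this review takes no view.

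The cost is a change of wording in the protocol and in the instructions given to subjects, with the usual amendment approval. No design quantity or analysis changes.

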### 5.3.2 Dose Escalation Rules and Definition of MTD

In Stage 1, each subject will be assigned to Dose Level 1 (40 mg/dose BID), Dose Level 2 (80 mg/dose BID), or Dose Level 3 (100 mg/dose BID) sequentially according to the dose level being explored at the time of subject enrollment. A Dose Level -1 (20 mg/dose BID) is provided in case a subject assigned to Dose Level 1 (40 mg/dose BID) requires dose reduction. In Stage 2, 8 subjects were enrolled at the Stage 1 MTD, Dose Level 2 (100 mg/dose BID). In Stage 3, each subject will be assigned to Dose Level 6 (160 mg/dose TID), or Dose Level 7 (200 mg/dose TID) sequentially according to the dose level being explored at the time of subject enrollment. Dose Level 5 (120 mg/dose TID) is provided in case a subject assigned to Dose Level 6 (160 mg/dose TID) requires dose reduction. Dose Level 4 (100 mg/dose BID) is provided in case a subject assigned to dose Level 5 (120 mg/dose TID) requires dose reduction.

During the study, dose escalation will depend on evaluations of safety in cycle 1 of therapy. The following dose escalation rules will be employed:

- Three subjects will be studied at the first dose level. If none of these three subjects experience DLT during cycle 1, then the dose will be escalated to the next higher level in the three subsequent subjects.
- If one of three subjects experiences DLT at the current dose during cycle 1, then three more subjects will be accrued at the same dose. If none of these three additional subjects experience DLT during cycle 1, then the dose will be escalated in subsequent subjects. If one or more of the three additional subjects experiences DLT in the first cycle, the MTD has been exceeded and three more subjects will be treated at the next lower dose (if only three subjects were previously treated at that prior dose).
- If two or more subjects experience DLT in the first cycle, then the MTD has been exceeded and three more subjects will be treated at the next lower dose level (if only three subjects were previously treated at that prior dose).
- No intrasubject dose escalations in subsequent cycles of therapy will be permitted.

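### Section 5.3.4 misprints the doses for Levels 6 and 7 in the next-cycle reduction rule: 120 and 160 mg TID instead of 160 and 200 mg TID

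*Combined protocol and SAP*

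**What the plan says.** Section 5.3.4 has two reduction rules for a subject who has a DLT.

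- **Within the same cycle.** After the event settles, the remaining doses of that cycle are cut by one level. For the top level the text is "reduction to Dose Level 6 (160 mg/dose TID) may be made for subjects experiencing PTC299-related DLT at Dose Level 7 (200 mg/dose TID".
- **In the next cycle.** Such subjects "should have the dose in the next cycle of therapy reduced by 1 dose level". The list that follows includes "reduction to Dose Level 6 (120 mg/dose TID) may be made for subjects experiencing PTC-related DLT at Dose Level 7 (160 mg/dose TID".

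The join between the two parts of the next-cycle list reads "DLT at Dose Level 5 (120 mg/dose TID) and reduction to Dose Level 6 (120 mg/dose TID) may be made".

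Section 5.3.2 defines the Stage 3 levels. There "each subject will be assigned to Dose Level 6 (160 mg/dose TID), or Dose Level 7 (200 mg/dose TID) sequentially", and "Dose Level 5 (120 mg/dose TID) is provided in case a subject assigned to Dose Level 6 (160 mg/dose TID) requires dose reduction". Section 5.3.6 converts levels to capsules of 20 mg: six per dose at Level 5, eight at Level 6 and ten at Level 7. The Schema names 160 and 200 mg TID as the two Stage 3 escalation doses.

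Two further provisions of Section 5.3.4 bear on the consequence. In general, "after a dose is reduced for PTC299-related toxicity it should not be re-escalated". Also, "If it takes longer than 4 weeks for the AE to resolve to baseline, protocol treatment will be permanently discontinued". Section 5.3.5 applies Section 5.3.4 to the Phase 2 portion.

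**The concern.** The next-cycle sentence pairs level numbers with doses in a way that nothing else in the protocol supports for Levels 6 and 7. It also attaches 120 mg TID to Level 5 and to Level 6 within a few words.

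This is an operating instruction, used by clinic staff to set the dose after a toxicity. Read by level number alone (7 to 6), or by milligrams alone (160 to 120 mg TID), it describes a one-level step, but the two steps start and end at different doses. Mixing the two, with the subject identified by level and the target taken in milligrams, sends a subject from 200 to 120 mg TID. That breaks the one-level rule in the same sentence.

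Level 7 may hold many of the Stage 3 subjects: if 200 mg TID is tolerated, Section 3.3.1 plans a total of 15 there. The trial is open to all AMC sites (Section 3.4), so different sites could resolve the conflict differently.

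**Working it through.** **1. Doses implied by the capsule counts.** Inputs: capsules per dose from Section 5.3.6, 20 mg per capsule, three doses a day.

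| Level | Capsules x 20 mg | Per dose | Per day (x 3) |
|---|---|---|---|
| 5 | 6 x 20 | 120 mg | 360 mg |
| 6 | 8 x 20 | 160 mg | 480 mg |
| 7 | 10 x 20 | 200 mg | 600 mg |

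**2. Each place that pairs Level 6 or 7 with a dose.**

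| Place | Level 6 | Level 7 |
|---|---|---|
| 5.3.2, Stage 3 assignment | 160 mg TID | 200 mg TID |
| 5.3.2, step down to Level 5 | 160 mg TID | not stated |
| 5.3.4, within-cycle rule | 160 mg TID | 200 mg TID |
| 5.3.6, capsule counts | 160 mg | 200 mg |
| 5.3.4, next-cycle rule | **120 mg TID** | **160 mg TID** |

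Leaving aside the capsule counts, Level 6 is printed as 160 mg TID three times and Level 7 as 200 mg TID twice. Only the next-cycle rule differs. Its figures cannot be reproduced from the capsule counts; they are the Level 5 and Level 6 doses, so the milligrams are one level too low for the labels.

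**3. Size of the mixed reading for a subject at Level 7.**

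- Intended step: 600 to 480 mg/day, 1 - 480/600 = 20%.
- Printed milligram target: 600 to 360 mg/day, 1 - 360/600 = 40%, two levels.
- Shortfall against the intended reduced dose: 1 - 360/480 = 25%.
- Per cycle of 28 x 3 = 84 doses: 8 x 84 = 672 capsules intended, 6 x 84 = 504 given. The difference is 168 capsules, or 168 x 20 = 3,360 mg.

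**4. How long it could last after a cycle 1 DLT.** Section 7.0 stops treatment after six cycles for subjects with no better than stable disease and allows up to twelve with a partial response.

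- Stable disease: at most 6 - 1 = 5 later cycles, 168 x 5 = 840 capsules (16,800 mg).
- Partial response: at most 12 - 1 = 11 later cycles, 168 x 11 = 1,848 capsules (36,960 mg).

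These are upper bounds, not expected losses. If the event takes more than 4 weeks to return to baseline, treatment ends and the question does not arise.

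**The case against.** The best case for leaving this as a minor note is that a careful site would get the dose right.

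- **Governing rule.** The instruction is a reduction of one level, and the list after it is permissive.
- **Dispensing.** Section 5.3.4 tells staff to give the subject the capsule number for the new dose level, and Section 5.3.6 maps Level 6 to eight capsules, which is 160 mg.
- **Neighbouring text.** The within-cycle rule in the same section prints the correct step.
- **Mixed reading.** Each consistent reading is a valid one-level step for some subject: 200 to 160 by level, 160 to 120 by milligrams. Harm needs the two to be mixed.
- **Shared doses.** One dose with two level numbers is not proof of error by itself, since 100 mg BID is deliberately both Level 3 and Level 4.

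All of this is fair, and it limits the consequence. It does not remove the conflict: the printed doses still contradict Sections 5.3.2 and 5.3.6 and the within-cycle rule.

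The within-cycle rule cuts both ways. A subject who resumes dosing in the same cycle is already down to 160 mg TID, so the case of a subject still at 200 mg TID fits best where dosing did not resume, or where the DLT was recognised at the end of the cycle. But a subject already at 160 mg TID also matches the misprinted sentence by milligrams, and staff could then move to 120 mg TID after a single DLT.

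The agreement elsewhere concerns Levels 6 and 7 only. Section 5.3.2 separately labels 100 mg BID as Level 2 when describing Stage 2; that slip is not relied on here.

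**Conclusion.** The concern holds. The next-cycle sentence is wrong as written: Level 6 should be 160 mg TID and Level 7 should be 200 mg TID. If its milligram target is followed for a subject at 200 mg TID, the daily dose is 360 mg instead of 480 mg, two levels down instead of one.

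This rests on two assumptions. The capsule counts and Section 5.3.2 are taken to state the intended levels, and the one-level step is taken from the dose at which the DLT occurred. No probability of misreading is claimed.

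The reach is limited. It concerns subjects with a DLT at Level 7 who continue treatment, and the error is towards a lower dose. The MTD rests on first-cycle DLTs by starting dose level (Section 5.3.2), so the MTD rule, the sample size and the power are unaffected. It should be corrected because it is a live dosing instruction that also governs Phase 2.

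**What to change.** In the next-cycle sentence of Section 5.3.4, change the Level 6 dose from 120 to 160 mg TID and the Level 7 dose from 160 to 200 mg TID, so that it agrees with the within-cycle wording: "reduction to Dose Level 6 (160 mg/dose TID) may be made for subjects experiencing PTC299-related DLT at Dose Level 7 (200 mg/dose TID". Nothing else has to change to remove the conflict.

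The cost is two numbers in one sentence. It needs no new data and no design change. Under Section 12.2 it goes through as a written amendment with CTEP and local IRB approval, and it can be carried in the next one.
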